6.1.2 Disease Status Monitoring

Disease status including requirement of supplemental oxygen, intensive care unit transfer, mechanical ventilation use, hospitalization and rescue therapy due to SARS-CoV-2 infection will be monitored during the study period (from signing of ICF to EOT).

6.1.2.1 Requirement of Supplemental Oxygen

The information of supplemental oxygen due to SARS-CoV-2 infection (at least 24 hours of supplemental oxygen care and SpO₂ measure in room air before applying supplemental oxygen shows $\leq 94\%$) during the study (from signing of ICF to EOT) will be recorded in the eCRF and source documents. Information to be collected includes the start and end date of supplemental oxygen, and type of supplemental oxygen delivery method (including but not limited to nasal prong, facial mask, and high-flow oxygen delivery).

6.1.2.2 Intensive Care Unit Transfer

The information of intensive care unit transfer due to SARS-CoV-2 infection during the study (from signing of ICF to EOT) will be recorded in the eCRF and source documents. Information to be collected includes the transfer and discharge date for the intensive care unit.

6.1.2.3 Mechanical Ventilation Use

The information of mechanical ventilation use due to SARS-CoV-2 infection during the study (from signing of ICF to EOT) will be recorded in the eCRF and source documents. Information to be collected includes the start and end date of mechanical ventilation use, and whether the patient has been intubated.

6.1.2.4 Hospitalization

The information of hospitalization due to SARS-CoV-2 infection during the study (from signing of ICF to EOT) for medical treatments (e.g. supplemental oxygen therapy and/or ≥ 24 hours of acute care, in a hospital or similar acute care facility) will be recorded in the eCRF and source documents. Information to be collected includes the start and end date of hospitalization due to SARS-CoV-2 infection.

6.1.2.5 Rescue Therapy

Rescue therapy is defined as the prohibited medication (defined in [Section 5.7](#)) administered due to SARS-CoV-2 infection after the study drug administration on Day 1.

The information of rescue therapy used due to SARS-CoV-2 infection after the study drug administration (Day 1) will be recorded in the eCRF and source documents.

6.1.3 National Early Warning Score 2

The information of National Early Warning Score 2 (NEWS2) ([Appendix 11.5](#)) assessed at the time points specified in the schedule of assessments ([Table 11-1](#) and [Table 11-2](#)) recorded in the eCRF and source documents.

6.2 Safety Assessments

6.2.1 Adverse Events

6.2.1.1 Definition of Adverse Events

The investigator is responsible for reporting all AEs that are observed or reported during the study, regardless of their relationship to study drug or their clinical significance.

An AE is defined as any untoward medical occurrence in any patient during the study which does not necessarily have to have a causal relationship with the study drug. Patients will be instructed to contact the investigator at any time after the ICF was signed if any symptoms develop ([Section 6.2.1.3](#)). Adverse events resulting from concurrent illnesses,

reactions to concurrent illnesses, reactions to concurrent medications, or worsening of the underlying disease or of other pre-existing conditions will be reported. In addition, changes in vital signs, physical examination, and laboratory tests will be recorded as (S)AE(s) in the eCRF if they are judged clinically significant by the investigator.

A treatment-emergent AE (TEAE) includes any untoward medical occurrence in a patient after administration of a study drug, which does not necessarily have to have a causal relationship with the study drug. This includes any occurrence that is new or aggravated in severity or frequency from the baseline condition. A TEAE can therefore be any unfavorable and unintended sign (including an abnormal laboratory finding), symptom, or disease temporally associated with the use of the product, whether or not related to the study drug.

Abnormal results of diagnostic procedures including laboratory test abnormalities are considered as AEs if they fulfill the following criteria:

- Result in discontinuation from the study drug
- Require treatment or any other therapeutic intervention
- Require further diagnostic evaluation (excluding a repetition of the same procedure to confirm the abnormality)
- Are associated with clinical signs or symptoms judged by the investigator to have a significant clinical impact
- Are clinically significant as evaluated by the investigator

Medical intervention such as surgery, diagnostic procedures, and therapeutic procedures are not AEs, but the action taken to treat the medical condition. They should be recorded as treatment(s) of the AEs. The event term of primary cause should be recorded and reported instead of the term of surgery, diagnostic procedure, or therapeutic procedure. For example, an acute appendicitis that begins during the AE reporting period should be reported as the AE, and the resulting appendectomy should be recorded as treatment of the AE.

6.2.1.1.1 Adverse Events of Special Interest

Infusion related reactions (hypersensitivity/anaphylactic reactions) is considered as AEs of special interest (AESI) because AE related to infusion related reactions (hypersensitivity/anaphylactic reactions) is typical of monoclonal antibody therapy, and will be reported using the same process as for AEs.

All AEs related to infusion related reactions (hypersensitivity/anaphylactic reactions) include but are not limited to the following: bronchospasm, larynx irritation, throat

irritation, hypotonia (collapse), syncope, incontinence, dizziness, vascular headache, generalized urticaria, rash, itch, flushing, swollen lips, swollen tongue, uvula swelling, angioedema, abdominal crampy pains, nausea, vomiting, hypotension, hypertension, tachycardia, bradycardia, palpitation, arthralgia, myalgia, and pyrexia (fever).

6.2.1.1.2 Serious Adverse Events

An SAE is defined as any untoward medical occurrence that at any dose:

- Results in death.
- Is life threatening (refers to an AE in which the patient was at immediate risk of death at the time of event). It does not refer to an event which may have caused death, if it was more severe.
- Requires inpatient hospitalization or prolongation of existing hospitalization.
- Results in persistent or significant disability/incapacity.
- Is a congenital anomaly/birth defect.

Medical and scientific judgment should be exercised in deciding whether expedited reporting is appropriate in other situations, such as important medical events that may not be immediately life-threatening or result in death or hospitalization but may jeopardize the patient or may require medical or surgical intervention to prevent one of the outcomes listed in the definition above. These should also be considered serious. Examples of such medical events include allergic bronchospasm requiring intensive treatment in an emergency room or at home, blood dyscrasias or convulsions that do not result in inpatient hospitalization, or the development of drug dependency or drug abuse.

Adverse events associated with hospitalization or prolongations of hospitalization are considered as SAEs. Any admission (even if <24 hours) to a healthcare facility meets these criteria. Admission also includes transfer within the hospital to an acute/intensive care unit (e.g., from the psychiatric wing to a medical floor, from medical floor to a coronary care unit, from neurological floor to a tuberculosis unit).

Hospitalization or prolongation of hospitalization in the absence of a precipitating clinical AE is not in itself an SAE. Examples include the following:

- Admission for treatment of a pre-existing condition not associated with the development of a new AE or worsening of the pre-existing condition (for work-up of persistent pre-treatment laboratory abnormality)
- Social admission (e.g., patient has no place to sleep)
- Purely for convenience (e.g., for easier performance of study assessments)
- Administrative admission (e.g., for yearly physical examination)

- Protocol-specified admission during a study (e.g., for a procedure required by the study protocol)
- Optional admission not associated with a precipitating clinical AE (e.g., for elective cosmetic surgery)
- Hospitalization for observation without a medical AE
- Pre-planned treatments or surgical procedures; these should be noted in the baseline documentation for the entire protocol and/or for the individual patient

6.2.1.1.3 Unlisted (Unexpected) Serious Adverse Events

An unlisted or unexpected SAE is defined as an event of which the nature or severity is not consistent with the applicable product information (e.g., IB) for an unapproved investigational product.

6.2.1.1.4 Suspected Unexpected Serious Adverse Events

The sponsor will promptly evaluate all SUSARs against cumulative product experience to identify and expeditiously communicate possible new safety findings to investigators, IRBs/IECs, and applicable health authorities based on applicable legislation.

To determine reporting requirements for single SAE cases, the sponsor will assess the expectedness of these events using the applicable reference documents (e.g., IB).

Reporting requirements will also be based on the investigator's assessment of causality and seriousness, with allowance for upgrading by the sponsor as needed.

6.2.1.2 Eliciting and Documenting Adverse Events

All AEs will be reported by the investigator via eCRF from the date patients signs the ICF until the last assessment date or EOT visit, regardless of the relationship to the study drug. Where an adverse drug reaction (ADR) (i.e., related to study drug) is ongoing at the EOT visit, the ADR will be followed up until one of the following: resolution or improvement from baseline, relationship reassessed as unrelated, confirmation from the investigator that no further improvement can be expected, end of collection of clinical or safety data, or final database closure.

At every study visit, patient will be asked a standard non-leading question to elicit any medically related changes in their well-being. They will also be asked if they have been hospitalized, had any accidents, used any new medications, or changed concomitant medication regimens (both prescription and over the counter medications).

In addition to patient's self-reporting of AEs ([Section 6.2.3](#)), AEs identified from any study data (e.g., laboratory values, physical examination findings, ECG changes) or identified from review of other documents that are relevant to patient safety will be documented on the AE page in the eCRF.

6.2.1.3 Reporting Adverse Events

All AEs reported or observed during the study (from signing of ICF to EOT) will be recorded on the AE page in the eCRF and source documents. Information to be collected includes drug treatment, dosage, action taken with study drug, event term, date/time of onset and end date, investigator-specified assessment of severity and relationship to study drug, seriousness of AE, any required treatment or evaluations, and outcome.

Adverse events resulting from concurrent illness, reactions to concurrent illnesses, or reactions to concurrent medications must also be reported. All AEs will be followed up to adequate resolution. Signs and symptoms of SARS-CoV-2 infection recorded in the patient diary throughout the study will not be reported as AEs. Further, worsening of SARS-CoV-2 infection which is considered as unrelated to the study drug will not be reported as an (S)AE.

Adverse events will be graded for severity according to [Common Terminology Criteria for Adverse Events \(CTCAE\) Version 5.0](#). The Medical Dictionary for Regulatory Activities (MedDRA) will be used to code all AEs.

Any medical condition which is present during Screening but does not deteriorate should not be reported as an AE. However, if it deteriorates at any time during the study, it should be recorded as an AE.

The investigator's assessment of an AE's relationship to study drug is part of the documentation process, but it is not a factor in determining what is or is not reported in the study. If there is any doubt as to whether a clinical observation is an AE, the event will be reported.

The severity and the relationship or association of the study drug in causing or contributing to the AE will be characterized as defined in [Section 6.2.1.6](#) and [Section 6.2.1.7](#), respectively.

After the EOT visit, serious adverse drug reactions will be reported to the sponsor, or its designee.

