The number and percentage of patients who discontinued the study in the Treatment Period will be presented by primary reason and treatment group. The number and percentage of patients who discontinued the study in the Follow-Up Period will also be displayed by primary reason and treatment group. The reasons for discontinuation will be displayed using the following categories and ordering:

- Adverse Event
- Lost to Follow-Up
- Death
- Investigator’s decision
- Withdrawal by Subject
- Other

In addition, the time on study prior to discontinuation will also be summarized using descriptive statistics by treatment group, if applicable, for those patients who have discontinued study prematurely in the Treatment Period or Follow-Up Period, respectively. The study duration in days will be calculated as (Date of last visit of each period - Date of study drug administration + 1).

The date of administration will be taken as the date on the “Study Drug Administration” page of the eCRF. Date of last visit of each period will be taken as the date on the “End of Treatment Period” or “End of Follow-up Period” page of the eCRF.

The patient disposition data collected for the ITT Set will be listed by treatment group.

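### Where sites apply the protocol's carve-out for unrelated SARS-CoV-2 worsening, the SAE-only Deaths listing in SAP 10.1.2 would omit COVID-19 deaths

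*Protocol*

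**What the plan says.** **The listing.** SAP 10.1.2 (Deaths) admits patients with an SAE whose serious criterion is death. It names no other source.

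**The carve-out.** Protocol 6.2.1.3 first keeps diary symptoms out of AE reporting. It then adds that "worsening of SARS-CoV-2 infection which is considered as unrelated to the study drug will not be reported as an (S)AE".

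**The general reporting rules.**
- Protocol 6.2.1.1: "worsening of the underlying disease or of other pre-existing conditions will be reported".
- Protocol 6.2.1.2: AEs are reported "until the last assessment date or EOT visit, regardless of the relationship to the study drug".
- Protocol 6.2.1.3, on a condition present at Screening: "if it deteriorates at any time during the study, it should be recorded as an AE".
- Protocol 6.2.1.3, repeated in 6.2.1.7, on the investigator's causality assessment: "it is not a factor in determining what is or is not reported in the study".

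**The end of collection.** Protocol 6.2.1.3: "All AEs reported or observed during the study (from signing of ICF to EOT) will be recorded on the AE page". It continues: "After the EOT visit, serious adverse drug reactions will be reported to the sponsor". SAP 10.1 instead runs AE collection to the end of each patient's participation. Note 24 of SAP Appendix 1 repeats the protocol's cut-off at the last assessment date or EOT.

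**Other places where deaths appear.** SAP 9.1 identifies SARS-CoV-2 deaths from the End of Treatment Period and End of Follow-Up Period pages of the eCRF. SAP 9.3 compares all-cause mortality up to Day 14 and up to Day 28. SAP 6 counts Death among the reasons for discontinuation by arm, and "The patient disposition data collected for the ITT Set will be listed by treatment group".

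**The concern.** A section headed Deaths in a safety analysis will normally be read as the complete record of deaths. Here its only entry route is an SAE record, and the protocol tells sites not to create that record for one foreseeable kind of death: progression of the disease under study, judged unrelated to the drug. The SAP already uses a broader source of deaths for efficacy than for this listing. The study report could therefore show fewer deaths in the listing than in its disposition and mortality outputs, with no explanation. Because no order of precedence is stated, two sites could also handle the same kind of death differently.

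**Working it through.** The plan states no figure on this point, so the check sets the passages side by side.

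**Step 1: what lets a death into the listing.** An SAE with death as the serious criterion is needed (SAP 10.1.2). SAP 12 records two changes to the planned analysis, one on membership of the ITTI Set and one on phenotype. Neither concerns deaths.

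**Step 2: when that SAE exists.** Protocol 6.2.1.1.2 makes a fatal untoward event an SAE. Protocol 6.2.1.3 then removes unrelated SARS-CoV-2 worsening.

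| Death | Rule followed | SAE expected | In Deaths listing |
|---|---|---|---|
| COVID-19, judged related, up to EOT | any | yes | yes |
| COVID-19, judged unrelated, up to EOT | general rules | yes | yes |
| COVID-19, judged unrelated, up to EOT | carve-out | no | no |
| Other cause, judged unrelated, after EOT | protocol window | not required | may be absent |
| Other cause, judged unrelated, after EOT | SAP 10.1 window | yes | yes |

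The third row is the core of the point. A COVID-19 death judged unrelated after EOT meets both obstacles.

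**Step 3: which protocol sentence governs.** The rules on worsening of underlying disease (6.2.1.1), on reporting regardless of relationship (6.2.1.2) and on conditions present at Screening (6.2.1.3) are general. A specific carve-out can sit beside them as an exception. The sentence on causality is harder to reconcile. It says that relatedness does not decide what is reported, whereas the carve-out makes relatedness the test. Both stand in 6.2.1.3, and neither refers to the other.

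**Step 4: when AE collection ends.** Protocol 6.2.1.2, Protocol 6.2.1.3 and SAP Appendix 1 note 24 stop at EOT, or at the last assessment date or EOT. SAP 10.1 continues to the end of participation. EOT is planned for Day 90 and follow-up runs to Day 180, so the planned gap is 180 − 90 = 90 days. It is longer for a patient who withdraws early and has EOT assessments sooner.

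**Step 5: whether the deaths are captured elsewhere.** They are. The two end-of-period pages record death as a reason for ending the period and feed both the composite endpoint and disposition. SAP 9.3 does not restrict all-cause mortality to deaths with an SAE. After Day 28, however, the disposition outputs are the main place where such a death would show.

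**Step 6: size.** The only rates given are for the composite of hospitalization, oxygen therapy or death due to SARS-CoV-2 up to Day 28:
- High-risk patients: 411 × 0.071 + 411 × 0.029 = 29.2 + 11.9 = about 41 events.
- All randomized patients: 650 × 0.055 + 650 × 0.025 = 35.75 + 16.25 = 52 events.

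Under those assumptions about 52 is a loose ceiling on SARS-CoV-2 deaths up to Day 28, since each such death is itself a composite event. It does not estimate deaths. The documents give no death rate, no share judged unrelated and no figure after Day 28. The number missing could be anything from zero to all SARS-CoV-2 deaths.

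**The case against.** The strongest defence is that the carve-out is deliberate. It follows directly on the exclusion of diary symptoms, and it covers the disease whose progression is the primary endpoint. Most of this stands: the general rules in 6.2.1.1 and 6.2.1.2 and the Screening-condition rule can all yield to it. The clash with the causality sentence remains. Accepting the defence also makes the listing gap firmer, because unrelated COVID-19 deaths are then left out by design.

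A second defence is that these deaths are reported elsewhere by arm. That stands, and it limits the point to one listing.

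Several stronger readings are tempting, but the documents do not support them:
- *Such deaths are missing outright.* This depends on a COVID-19 death, judged unrelated, at a site that applies the carve-out. A site following the general rules would file an SAE.
- *Any mismatch with disposition must come from the SAE-only source, since both listings use the ITT Set.* SAP 6 tabulates one primary reason per discontinuation, with Adverse Event and Death as separate categories. A fatal SAE filed under another reason would also produce a mismatch.
- *The SAP simply departs from the protocol on the end of AE collection.* Appendix 1 note 24 repeats the protocol's rule, so the SAP contradicts itself. The Follow-Up Period value of the period flag proves nothing here, because serious adverse drug reactions after EOT need it anyway.
- *The DSMB would not see these deaths.* Protocol 9.4 refers to review of SAE listings, but also to evaluation of available data, and leaves details to the charter. The documents do not settle this.

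**Conclusion.** The concern holds in a limited, conditional form. Followed as written, SAP 10.1.2 and the carve-out in Protocol 6.2.1.3 together leave COVID-19 deaths judged unrelated out of the safety Deaths listing. Unrelated deaths after EOT may be absent as well. The extent is one listing, which may be incomplete, inconsistent between sites and at odds with the disposition and mortality outputs. The deaths are not lost from the trial data, and no efficacy estimate, sample size or error rate is affected.

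The conclusion assumes that the listing is programmed from SAEs alone, as the SAP says, and that at least some sites apply the carve-out to fatal cases. The documents do not show how often that would happen. The point is worth correcting because the remedy is cheap, but it is no reason to doubt the trial's main result.

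**What to change.** 1. **SAP 10.1.2.** List every ITT patient with a death recorded on the End of Treatment Period page, on the End of Follow-Up Period page, or as an SAE with death as the serious criterion, counting each patient once. Take cause of death from the sources already named in SAP 9.1. Leave fields blank where no SAE record supplies them: the documents name no other source for date of death, autopsy or death certificate, so complete rows cannot be promised. Compare the result with the Death counts in SAP 6 and explain any differences. Equality should not be required, because disposition records a single primary reason.
2. **Protocol.** Reconcile the carve-out in 6.2.1.3 with 6.2.1.1, with 6.2.1.2 and with the causality sentence in 6.2.1.3 and 6.2.1.7, and state which takes precedence. The choice is the sponsor's.
3. **End of AE collection.** Align Protocol 6.2.1.2 and 6.2.1.3 with SAP 10.1 and SAP Appendix 1 note 24.

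The cost is a short change to SAP 10.1.2 using eCRF pages already collected, one comparison at reporting, and clarifying text in both documents. No efficacy analysis changes.

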6.2.1.4 Reporting Serious Adverse Events

Any AE considered serious by the investigator or which meets SAE criteria ([Section 6.2.1.1.2](#)) must be reported to CRO within 24 hours from the time the investigator or designee first learn about the event and during normal business hours. The following contact information is to be used for SAE reporting:

Medical Affairs/Pharmacovigilance

PPD PVG

EMEA/APAC SAE Hotline:

[REDACTED]

NA back-up SAE Hotline (IDMC):

[REDACTED]

LA SAE Hotline:

[REDACTED]

EMEA/APAC SAE Fax line:

[REDACTED]

NA back-up SAE Fax line (IDMC):

[REDACTED]

LA SAE Fax line:

[REDACTED]

SAE E-mail:

[REDACTED]

Data entry should be completed in the remote data capture system by the investigator within 24 hours of awareness of an SAE. In the event that this is not possible (e.g., system failure or access problems), the study center should complete an SAE report form and email the form to CRO [REDACTED] or fax it to CRO within 24 hours of awareness of the event. The remote data capture system should be updated as soon as it is available. Withdrawal from the study and all therapeutic measures will be at the discretion of the principal investigator or sub-investigator. All SAEs (regardless of relationship with the study drug) will be followed up until satisfactory resolution or until the investigator deems the event to be chronic or not clinically significant or the patient to be stable.

The sponsor or its designee is responsible for reporting relevant SAEs to the competent authority, other applicable regulatory authorities, and participating investigators, in accordance with European Clinical Trials Directive (Directive 2001/20/EC), ICH guidelines, and/or local regulatory requirements.

The sponsor or its designee is responsible for reporting fatal or life-threatening SUSAR (expedited reports) to the regulatory agencies and competent authorities within 7 calendar days after being notified of the event. The sponsor or its designee should report other relevant SAEs associated with the use of the study drug to the appropriate competent authorities (according to local guidelines), investigators, and IRBs/IECs by a written safety report within 15 calendar days of notification.

